Appendix B: Analysis Visit Windows for Safety and Efficacy Assessments

Table 11-4 Analysis Visit Windows for Safety and Efficacy Assessments			
Assessment	Visit^a	Target Study Day^b	Analysis Visit Window (in study days)
Safety Assessment (Part 1)			
Serum Chemistry Hematology Vital Signs (excluding Weight)	Day 1 (Baseline)	1	≤1 Pre-dose
	Day 15	15	[1, 22]
	Day 29	29	Use nominal visit, otherwise use (22, 31]
	Day 33	33	Use nominal visit, otherwise use (31, 47]
	Safety Follow-up	61	Use nominal visit
Coagulation Vital Signs (Weight only)	Day 1 (Baseline)	1	≤1 Pre-dose
	Day 15	15	[1, 22]
	Day 29	29	(22,45]
	Safety Follow-up	61	Use nominal visit
Standard 12-lead ECG	Day 1 (Baseline; before dosing)	1	Use nominal visit for all visits
	Day 1 (5 hours after dosing)	1	
	Day 15 (before dosing and 5 hours after dosing)	15	
	Day 29	29	
	Safety Follow-up	61	
Spirometry	Day 1 (5 hours post dose)	1	Use nominal visit
	Day 15 (5 hours post dose)	15	Use nominal visit
Safety Assessment (Part 2)			
Serum Chemistry Hematology Vital Signs (including Weight)	Day 1 (Baseline)	1	≤1 Pre-dose
	Day 15	15	[1,22]
	Day 29	29	(22, 36]
	Day 43	43	(36, 50]
	Day 57	57	(50, 71]
	Safety Follow-up	85	Use nominal visit
Coagulation	Day 1 (Baseline)	1	≤1 Pre-dose
	Day 15	15	[1,22]
	Day 29	29	(22, 57]
	Safety Follow-up	85	Use nominal visit
Standard 12-lead ECG	Day 1 (Baseline; before dosing)	1	Use nominal visit for all visits
	Day 1 (5 hours after dosing)	1	
	Day 15 (before dosing and 5 hours after dosing)	15	
	Day 29	29	
	Day 43	43	
	Day 57	57	
	Safety Follow-up	85	

Table 11-4 Analysis Visit Windows for Safety and Efficacy Assessments			
Assessment	Visit^a	Target Study Day^b	Analysis Visit Window (in study days)
Spirometry	Day 1 (5 hours post dose) Day 15 (5 hours post dose)	1 15	Use nominal visit Use nominal visit
Safety Assessment (Part 3)			
Serum Chemistry	Day 1 (Baseline)	1	≤1 Pre-dose
Hematology	Day 15	15	[1,22]
Coagulation	Day 29	29	(22, 43]
Vital Signs (including Weight)	Safety Follow-up	57	Use nominal visit
Standard 12-lead ECG	Day 1 (Baseline; before dosing) Day 1 (5 hours after dosing) Day 15 (before dosing and 5 hours after dosing) Day 29 Safety Follow-up	1 1 15 29 57	Use nominal visit for all visits
Spirometry	Day 1 (5 hours post dose) Day 15 (5 hours post dose)	1 15	Use nominal visit Use nominal visit
Efficacy Assessment (Part 1)			
Spirometry	Day 1 (Baseline; before dosing)	1	≤1 Pre-dose
Sweat Chloride	Day 15 (predose)# Day 29 Day 33 Safety Follow-up	15 29 33 61	[1, 22] Use nominal visit, otherwise use (22, 31] Use nominal visit, otherwise use (31, 47] Use nominal visit
CFQ-R	Day 1 Day 15 Day 29	1 15 29	≤1 [1, 22] (22, 45]
Efficacy Assessment (Part 2)			
Spirometry	Day 1 (Baseline; before dosing)	1	≤1 Pre-dose
Sweat Chloride	Day 15 (predose)#	15	[1,22]
CFQ-R	Day 29 Day 43 Day 57 Safety Follow-up (Spirometry only)	29 43 57 85	(22, 36] (36, 50] (50, 71] Use nominal visit
Efficacy Assessment (Part 3)			
Spirometry	Day 1 (Baseline; before dosing)	1	≤1 Pre-dose
Sweat Chloride	Day 15 (predose)#	15	[1,22]
CFQ-R	Day 29 Safety Follow-up (no CFQ-R)	29 57	(22, 43] Use nominal visit
Notes:			
^a Visit name is used to report data in tables, listings and figures.			
^b Target day time point per protocol is predose, except for ECG and SP measurements.			

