8 STATISTICAL ANALYSIS

8.1 General Considerations

The analysis will be performed for each part, and presented by treatment group and overall, for the Treatment Period, unless specified otherwise. The treatment groups are defined as follows:

- Part 1: *F508del*/MF genotype group
 - Placebo, TC-low, TC-mid, and TC-high.
- Part 2: *F508del*/*F508del* genotype group
 - TEZ/IVA and TC-high.
- Part 3: *F508del*/MF genotype group
 - Placebo and TC2-high.

The Schedule of Assessments is provided in [Appendix A](#). The precision standards for reporting safety and efficacy variables are provided in an internal Biometrics document that specifies the programming rules including the precision for derived variables.

All individual subject data for those randomized or dosed with any amount of study drug will be presented in data listings.

Continuous variables will be summarized using the following descriptive summary statistics: the number of subjects (n), mean, SD, standard error (SE), median, minimum value (min), and maximum value (max). SE may not be reported for safety summary tables.

Categorical variables will be summarized using counts and percentages. Percentages will be presented to 1 decimal place.

Baseline value, unless otherwise specified, will be defined as the most recent non-missing measurement (scheduled or unscheduled) collected before the first dose of study drug on Day 1 of the Treatment Period. For ECG, baseline will be defined as the most recent non-missing measurement (or the average of triplicate measurements, if the most recent non-missing measurement is obtained in triplicate), before the first dose of study drug on Day 1 of the Treatment Period.

Absolute change from baseline will be calculated as postbaseline value – baseline value.

Relative change from baseline will be calculated as (postbaseline value – baseline value)/baseline value.

Treatment-emergent (TE) period for Parts 1 and 3 will be from the first dose date of study drug in the Treatment Period until 28 days after the last dose date of study drug or end of study date (based on end of study visit in CRFs), whichever occurs first.

For Part 2, the TE period will be defined separately for the Run-In Period, and the Treatment Period:

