8.3.1.1 Primary Analysis of the Primary Efficacy Variable

8.3.1.1.1 All Parts: Period 1 in the Treatment Period

The null hypothesis to be tested is that the mean absolute within-group change from baseline in ppFEV₁ through Day 29 is zero for VX-659 in TC with TEZ and either IVA or VX-561, for each part, separately. A 2-sided *p*-value of 0.05 or less will be interpreted as sufficient evidence to reject the null hypothesis.

The primary analysis will be performed using a mixed-effects model for repeated measures (MMRM) with change from baseline in ppFEV₁ as the dependent variable for each part, separately. For Part 1, the analysis will include 4 treatment groups: placebo, TC-low, TC-mid, and TC-high. For Part 2, the analysis will include 2 treatment groups: placebo + TEZ/IVA, and TC-high (VX-659 + TEZ/IVA). For Part 3, the analysis will include 2 treatment groups: placebo and TC2-high (VX-659+TEZ+VX-561). The model will include treatment group, visit, and treatment-by-visit interaction as fixed effects and subject as a random effect, with the continuous baseline ppFEV₁ as a covariate, and will include all data from each treatment group and visit during Period 1 in the analysis. The model will be estimated using restricted maximum likelihood. Denominator degrees of freedom for the F test for fixed effects will be estimated using the Kenward-Roger approximation. An unstructured covariance structure will be used to model the within-subject errors. If the model estimation does not converge, a reduced compound symmetry covariance structure will be used instead. Conditional on the observed data and covariates, missing ppFEV₁ data due to treatment or study discontinuation will be assumed to be missing at random; consequently, no imputation of missing data will be performed.

[figure not shown]
The adjusted means and 95% confidence intervals (CI) of the average treatment effect through Day 29 for each TC, with a 2-sided *p*-value will be estimated within MMRM using PROC MIXED in SAS, for all within-treatment and between-treatment comparisons, for each part, separately. Contrasts based on the fixed effects in the model, defined at the baseline covariate mean for the combined treatment groups using unique subjects in the FAS who have at least one post-baseline measurement through Day 29, will be used to estimate the average treatment effect across post-baseline visits through Day 29.

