Further, the adjusted mean and 95% CI of the treatment difference between each TC group and placebo or TEZ/IVA at each post-baseline visit through Day 29 will be provided along with the corresponding *p*-value, for each part. In addition, the adjusted mean and 95% CI of the within-treatment difference at each post-baseline visit through Day 29 for each treatment group will be provided along with the *p*-value, for each part.

The adjusted mean (with 95% CI) obtained from the MMRM analysis at each post-baseline visit through Day 29 will be plotted by treatment group, for each part. In addition, a waterfall plot showing the subject-level absolute change in ppFEV₁ at Day 29 will be presented, by treatment group.

The primary analysis will use pre-dose measurements only. The post-dose measurements on the same day will be used for sensitivity analysis as described in the next section.

In addition, for each part, descriptive analyses of the change from baseline will be performed for all treatment groups by post-baseline visit through the safety follow-up visit.

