# Postdose of spirometry may be used for imputation			
The analysis visit windows will be applied using the following rules for both scheduled and unscheduled visits:			
1. If no numerical measurement is available within a visit window, the measurement will be considered			

Table 11-4 Analysis Visit Windows for Safety and Efficacy Assessments			
Assessment	Visit^a	Target Study Day^b	Analysis Visit Window (in study days)

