			
missing for the visit.
 
2. If there is more than 1 numerical measurement available within the same visit window, use the following rules:
 
a. For efficacy parameters: if there are multiple measurements within a visit window, the measurement at the scheduled visit will be used. Otherwise,
 
i. If there are no measurements at the scheduled visit, then the measurement closest to the target day will be used; or
 
ii. If there are multiple measurements with the same distance to the target day, the latest measurement will be used.
 
b. For safety parameters: if there are multiple measurements within a visit window,
 
i. The measurement closest to the target day will be used; or
 
ii. If there are multiple measurements within the same distance from the target day, the latest measurement will be used.
 
iii. For tables of extreme lab measurements based on ULN or LLN, convert the lab measurements into \timesULN or \timesLLN first, and then select the extreme measurement.
 
Derived Variables:
 
1. Age (in years) at first dose date
 
Obtain age at screening (in days) in yy mm format (e.g., 24 years, 6 months) from screening vital signs page, and add 0.5 month to convert to days.
 
Obtain screening date from Date of Visit (DOV) page.
 
Then age (in years) at first dose date = integer part of $\{[(\text{first dose date}-\text{screening date}) \text{ in days} + \text{age at screening (in days)}]/365.25\}$.
 
Correspondingly, age (in months) at first dose date = integer part of $12 * \{[(\text{first dose date}-\text{screening date}) \text{ in days} + \text{age at screening (in days)}]/365.25\}$.
 
2. Age (in years) at post-baseline visit (for use in calculation of percent predicted spirometry variables)
 
Age (in years) at post-baseline visit = $[(\text{post-baseline visit date} - \text{screening date}) \text{ in days} + \text{age at screening (in days)}]/365.25$
 
3. Missing First Dose Date or Last Dose Date
 
If the first dose date is missing, use Day 1 visit date.
 
If the last dose date is missing at final analysis, use maximum of Early Treatment Termination (ETT) visit date and last study drug administration date from EX SDTM domain (excluding PK dosing dates). When a subject is lost to follow up without ETT, impute the last dose date as the last treatment period visit date.
 
4. Missing Date for Drug Interruption
 
If the dates for drug interruption are completely missing or partially missing and it cannot be determined in which period the interruption occurred, then assume the interruption occurred during the Treatment Period (Period 1) for 1 day.
 
5. Sweat Chloride:
 
The qualified left arm and right arm SWCL assessments on Day 1 with end date/time for a given arm up to 30 minutes after first dose time will be considered for baseline. If Day 1 value is unavailable or invalid, screening value will qualify as baseline.

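### The Day 15 analysis window in SAP Table 11-4 includes Day 1 and overlaps the baseline window, so read literally a Day 1 value can stand in for a missing Day 15 value

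*SAP*

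**What the plan says.** **Windows (SAP Appendix B, Table 11-4).** Baseline for spirometry and sweat chloride is study day 1 or earlier, pre-dose. CFQ-R has the same baseline window in Parts 2 and 3; in Part 1 it is day 1 or earlier with no dose qualifier. The Day 15 window is [1, 22] in every part, for these efficacy measures and for chemistry, hematology, coagulation and vital signs. The Part 1 spirometry and sweat chloride cells for Day 15 and Day 29 read "1, 22] Use nominal visit, otherwise use (22, 31", with a square bracket opening before the 1 and closing after the 31. ECGs go by nominal visit and are not affected.

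**Selection rules (same appendix).** A visit counts as missing only when its window holds no numerical value. When there are several efficacy values, "the measurement at the scheduled visit will be used". Failing that, "If there are no measurements at the scheduled visit, then the measurement closest to the target day will be used". For safety parameters the closest value is taken directly.

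**Text that bears on the overlap.** Section 8.1 defines baseline as the latest value "collected before the first dose of study drug on Day 1 of the Treatment Period", and adds: "Absolute change from baseline will be calculated as postbaseline value – baseline value". Section 8.3.1.1.1 says "The primary analysis will use pre-dose measurements only" and, under missing at random, "consequently, no imputation of missing data will be performed". The # note, attached to the Day 15 (predose) efficacy rows, says "Postdose of spirometry may be used for imputation". It names neither a day nor an analysis.

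**The concern.** A pre-dose record on study day 1 satisfies both the baseline window and the Day 15 window. SAP section 8.3 sends the efficacy analyses through these windows, and nothing in the rules says that a record used as baseline leaves the Day 15 pool. A programmer following the table to the letter would find that Day 15 is never missing for anyone with a day 1 record. Where it should be missing, the change would be exactly 0.

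That is baseline carried forward, where the plan intends the MMRM to treat the value as missing at random. In active arms it pulls the average through Day 29 toward no effect. For sweat chloride it also feeds the Part 1 dose-response test. In by-visit safety tables it pulls changes toward zero, which is not the cautious direction. The # note opens a second route, by which post-dose spirometry might fill Day 15.

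**Working it through.** **1. How the windows were built.** Most numeric bounds are midpoints between adjacent target days:

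- (15 + 29)/2 = 22
- (29 + 33)/2 = 31
- (29 + 43)/2 = 36
- (43 + 57)/2 = 50

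The midpoint rule would start Day 15 at (1 + 15)/2 = 8. The table starts it at 1, apparently so that all early post-baseline data fall in Day 15. Every later numeric window has an open lower bound, for example (22, 31] then (31, 47]. Only the Day 1/Day 15 boundary is closed on both sides.

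**2. Which records fall where.**

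| Record | Baseline window | [1, 22] | (1, 22] | Distance from Day 15 |
|---|---|---|---|---|
| Day −1 | yes | no | no | 16 |
| Day 1 pre-dose | yes | **yes** | no | 14 |
| Day 1 post-dose | no | **yes** | no | 14 |
| Day 2 | no | yes | yes | 13 |
| Day 22 | no | yes | yes | 7 |

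**3. When Day 1 would be chosen.** Within [1, 22], Day 1 is the farthest day from the target. It is reached only if there is no usable scheduled Day 15 value and nothing else on Days 2 to 22, such as an unscheduled or early-termination (ETT) value.

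**4. Where that can happen.**

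- *CFQ-R.* It is not scheduled at the ETT Visit (SAP Tables 11-1 to 11-3). After discontinuation before Day 15, the Day 1 questionnaire may be the only one in the window.
- *Sweat chloride.* SAP section 8.3.5 sets low-volume samples and values below 10 or above 160 mmol/L to missing. An invalid Day 15 sample with no other value on Days 2 to 22 falls back to Day 1. An ETT value in the window would prevent this.
- *Laboratory tests and vital signs.* The same fallback applies; these too are collected at the ETT Visit.
- *Spirometry.* An ETT value in the window displaces Day 1. Section 8.3 keeps same-day post-dose values out of model-based analyses other than sensitivity analyses. A Day 1 pre-dose value is the baseline, not a postbaseline value.

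The schedule lets the Day 1 sweat chloride and CFQ-R be done on Day −1 after randomization. Such a record lies outside [1, 22], so the overlap does not then arise. Spirometry does not carry that footnote.

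**5. Size on the literal reading.** Inputs are the 7-point change and 18 per group from SAP section 6.2.1.2, and 9 in TC-low from the 1:1:2:2 ratio with 54 subjects. Assume a true mean change of 7 at Day 15 and Day 29.

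- One subject with Day 15 set to 0 and Day 29 observed: shift in the two-visit average = 7/n/2. For n=18, 7/18/2 = 0.19 (7 falls to 6.81). For n=9, 7/9/2 = 0.39 (7 falls to 6.61).
- Two of 18 affected: 2 × 7/18/2 = 0.39 (7 falls to 6.61).
- One subject with Day 15 set to 0 and Day 29 missing: the Day 29 mean also moves, by about ρ × 7/n, where ρ is the between-visit correlation (equal variances assumed). The shift is (7/n)(1 + ρ)/2. The documents give no ρ. For ρ from 0.5 to 0.9 it is 0.29 to 0.37 (n=18) or 0.58 to 0.74 (n=9).

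**The case against.** The strongest reply is that the SAP already prevents the harm. Change is computed from a postbaseline value, and the section 8.3.1.1.1 contrasts average over post-baseline visits, so reusing the baseline record contradicts both. Since the baseline window is marked pre-dose, the 1 in [1, 22] can be read as Day 1 after dosing. The 5-hour Day 1 spirometry value has its own safety row and is barred from the primary model. Sweat chloride ending up to 30 minutes after first dose is assigned to baseline. CFQ-R is a Day 29 endpoint, so its Day 15 value matters only indirectly. The # note may belong to a sensitivity analysis: section 8.3.1.1.1 refers to one in its next section, which is not in the public text.

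Much of this stands. A reader might infer that any missing Day 15 ppFEV1 is replaced by baseline, or that a subject who leaves before Day 15 enters the primary model with a zero change. The documents do not support either. The fallback needs an empty Days 2 to 22, an ETT value would usually fill that gap, and sections 8.1, 8.3 and 8.3.1.1.1 point against both Day 1 values.

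What does not fall away is the table itself. No windowing rule excludes the baseline record, the Day 15 cells carry no post-dose qualifier, and two competent programmers could code them differently. The # note, as printed, is not confined to a sensitivity analysis.

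**Conclusion.** The point holds as a defect in a stated rule with small expected impact. The Day 15 window overlaps the baseline window in all three parts and, read literally, can turn a missing Day 15 value into a change of 0. This is most plausible for CFQ-R, sweat chloride and by-visit laboratory and vital-sign data. For primary ppFEV1 it is a risk of literal wording, not a demonstrated bias. The # note does conflict, as written, with the pre-dose-only and no-imputation statements.

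One affected subject costs 0.19 of 7 points in an arm of 18 and 0.39 in an arm of 9, with Day 29 observed and a true change of 7 at both visits. The n=9 figure applies to TC-low only: the other arms of nine are controls, for which the plan assumes no 7-point effect. In active arms the efficacy direction is conservative. The documents do not say how often Days 2 to 22 would be empty; few such subjects are expected, given the ETT Visit. The point does not depend on the power statement.

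**What to change.** In SAP Table 11-4:

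1. Change every Day 15 efficacy window to (1, 22].
2. For laboratory tests and vital signs, use either (1, 22] or Day 1 post-dose through Day 22. The second keeps a window for unscheduled Day 1 post-dose values.
3. Add a rule that a baseline record cannot also serve as a post-baseline value.
4. Limit the # note to the same-day Day 15 post-dose value, in the sensitivity analysis only.

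A subject with nothing on Days 2 to 22 is then missing at Day 15, as section 8.3.1.1.1 intends. The cost is a few brackets and two sentences, with no change to data collection. The one downside is that an unscheduled Day 1 post-dose efficacy value can no longer fill Day 15.

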- ^f On days of scheduled visits, the in-clinic dose of study drugs will be given in the morning, at least 6 hours apart from any other scheduled dose and after all predose assessments are complete. The last dose of VX-659 and TEZ/VX-561 in Part 3 Period 1 will be the morning dose on the Day 29 Visit. Refer to Section 9.7 for details.
- ^g CFTR genotyping will be performed for all subjects. If the screening CFTR genotype result is not received before randomization, a previous CFTR genotype laboratory report may be used to establish eligibility (see inclusion criterion 6).
- ^h Weight and height will be measured with shoes off.

Table 3-3 Study VX16-659-101 Part 3 (Subjects with F/MF genotypes): Schedule of Assessments

Event/Assessment ^a	Screening Period		Treatment Period (4 weeks)			ETT Visit ^b	Safety Follow-up 28 (± 7) Days After Last Dose
			Period 1 ^c (4 weeks)				
	Screening Visit Days -28 to -1	Stratification Visit ^d Days -27 to-3	Day 1	Day 15 (± 2 days)	Day 29 (± 2 days)		
Physical examination ⁱ	Complete		Abbrev.	Abbrev.	Abbrev.	Abbrev.	Complete
Vital signs ^j	X		X	X	X	X	X
Pulse oximetry ^j	X		X	X	X	X	X
Standard 12-lead ECG ^k	X		X	X	X	X	X
Sweat chloride ^{l,o}	X		X	X	X	X	X
Spirometry ^m	X	X	X	X	X	X	X
CFQ-R ^{n,o}			X	X	X		
Urinalysis ^o	X		X	X	X	X	X
Pregnancy test (females of childbearing potential)	Serum		Urine		Urine	Serum	Serum
FSH ^p	X						

ⁱ Complete and abbreviated physical examinations (PEs) are described in Section 11.7.3. Symptom-directed PEs can be done at any time at the discretion of the investigator or healthcare provider.

^j Vital signs and pulse oximetry will be collected after the subject has been seated for at least 5 minutes.

^k Standard 12-lead ECGs will be performed after the subject has been rested for at least 5 minutes. On the Day 1 and 15 Visits, ECGs will be collected before dosing and 5 hours (± 1 hour) after dosing. At other visits, ECGs will be collected before dosing (as applicable). ECGs collected on the Day 1 Visit before dosing will be performed in triplicate.

^l See inclusion criterion 5 for information about the sweat chloride assessment for study eligibility. Sweat chloride assessments should be done at approximately the same time at every study visit during the Treatment Period and follow-up.

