	Screening Visit Days -56 to -29	Day -28 (± 1 day)	Day -14 (Days -15 to -3)	Day 1	Day 15 (± 2 days)	Day 29 (± 2 days)	Day 43 (± 3 days)	Day 57 (± 3 days)		
Informed consent	X									
Randomization ^e				X						
Study drug dosing ^f		Day -28 to Day -1		Day 1 to 29			Day 29 to 57			
Demographics	X									
Medical history	X									
CFTR genotype ^g	X									
Height ^h	X									
Weight ^h	X	X		X	X	X	X	X	X	X
Physical examination ⁱ	Complete	Complete	Abbrev.	Abbrev.	Abbrev.	Abbrev.		Abbrev.	Abbrev.	Complete
Vital signs ^j	X	X		X	X	X	X	X	X	X

^a All assessments will be performed predose, unless noted otherwise. Assessments that are collected predose and postdose will only be collected once if study drug is not administered on the day of the visit (i.e., if subject prematurely discontinued study drug treatment).

^b If the subject prematurely discontinues study drug treatment, an Early Termination of Treatment (ETT) Visit should be scheduled as soon as possible after the decision to discontinue study drug treatment. Subjects who prematurely discontinue treatment will be required to complete the Safety Follow-up Visit. If the ETT Visit occurs 3 or more weeks after the last dose of study drug, the ETT Visit will replace the Safety Follow-up Visit (a separate Safety Follow-up Visit is not required).

^c Part 2 subjects who meet criteria specified in Section 9.1.5 will not have a Safety Follow-up Visit.

^d To be eligible to continue into the Treatment Period, subjects must have stable CF disease and have remained on stable CF medication regimen during the 28 days before the Day 1 Visit AND must not have had an acute non-CF illness within 14 days before the Day 1 Visit. See Section 9.1.4.

^e Randomization may occur on the previous day (Day -1) after all inclusion and exclusion criteria and criteria for entry into the Treatment Period (see footnote d) have been confirmed.

^f On days of scheduled visits, the in-clinic dose of study drug will be given in the morning, at least 6 hours apart from any other scheduled dose and after all predose assessments are complete. The last dose of VX-659 in Part 2 Period 1 will be the morning dose on the Day 29 Visit. The last dose of TEZ/IVA in Part 2 Period 2 will be the morning dose on the Day 57 Visit. Refer to Section 9.7 for details.

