^m The ppFEV1 assessment for stratification of randomization will be done at the Day -14 Visit. See Section 9.3.1. At the Screening Visit, spirometry may be done pre- or post-bronchodilator. At other study visits, spirometry will be done pre-bronchodilator, before the in-clinic dose of study drugs, and should be performed at approximately the same time at every visit. On the Day 1 and 15 Visits, spirometry will also be performed 5 hours (± 1 hour) after the in-clinic dose of study drugs.

ⁿ CFQ-R must be completed before the start of any other assessments scheduled at that visit.

^o The predose assessment on the Day 1 Visit may be performed on the previous day (Day -1) if randomization has occurred.

^p FSH will be measured for any suspected postmenopausal female subjects with at least 12 months of continuous spontaneous amenorrhea.

^q Blood samples will be collected for the G6PD activity test.

Table 11-2 Study VX16-659-101 Part 2 (Subjects with F/F genotype): Schedule of Assessments

Event/Assessment ^a	Screening Period	Run-in (4 weeks)		Treatment Period (8 weeks)				ETT Visit ^b	Safety Follow-up 28 (± 7) Days After Last Dose ^c
				Period 1 (4 weeks) ^d		Period 2 (4 weeks)			
	Screening Visit Days -56 to -29	Day -28 (± 1 day)	Day -14 (Days -15 to -3)	Day 1	Day 15 (± 2 days)	Day 29 (± 2 days)	Day 43 (± 3 days)	Day 57 (± 3 days)	
PK sampling ^r				X	X	X	X	X	
AEs, medications, treatments, and procedures	Continuous from signing of the ICF through the Safety Follow-up Visit								

^r Blood samples will be collected for PK analysis of study drugs and metabolites. On the Day 1 Visit, samples will be collected before (0 hours) and 1, 2, 4, and 6 hours after the in-clinic dose. On the Day 15 Visit, samples will be collected before (0 hours) and 1, 2, 4, 6, and 8 hours after the in-clinic dose. On the Day 29 and 43 Visits, a single sample will be collected before the in-clinic dose. At the ETT Visit, a single sample will be collected.

Refer to Section 9.5 for details.

Table 11-3 Study VX16-659-101 Part 3 (Subjects with F/MF genotypes): Schedule of Assessments

Event/Assessment ^a	Screening Period		Treatment Period (4 weeks)			ETT Visit ^b	Safety Follow-up 28 (± 7) Days After Last Dose
			Period 1 ^c (4 weeks)				
	Screening Visit Days -28 to -1	Stratification Visit ^d Days -27 to-3	Day 1	Day 15 (± 2 days)	Day 29 (± 2 days)		
Informed consent	X						
Randomization ^e			X				
Study drug dosing ^f			Day 1 through Day 29 Visit				
Demographics	X						

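### In Parts 2 and 3, and for CFQ-R in Part 1, the Day 29 efficacy window extends past the end of VX-659 dosing, so a dosing completer with no valid scheduled Day 29 value can have a post-VX-659 value analysed as Day 29

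*SAP*

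**What the plan says.** The windows are in SAP Appendix B, Table 11-4, efficacy rows.

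- Part 3 (spirometry, sweat chloride, CFQ-R): from the Day 29 limit on, the entries read "22, 43] Use nominal visit". The Day 29 window is (22, 43]. The words after the bracket are the next row, Safety Follow-up.
- Part 2 (same three endpoints): "22, 36] (36, 50] (50, 71" gives the Day 29, Day 43 and Day 57 windows in turn, so Day 29 is (22, 36].
- Part 1, spirometry and sweat chloride: "Use nominal visit, otherwise use (22, 31", that is, Day 31 at the latest unless the value comes from the nominal visit.
- Part 1, CFQ-R: (22, 45].

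The schedules of assessments place the Day 29 Visit at Day 29 ± 2 and end VX-659 there. For Part 2: "The last dose of VX-659 in Part 2 Period 1 will be the morning dose on the Day 29 Visit". For Part 3: "The last dose of VX-659 and TEZ/VX-561 in Part 3 Period 1 will be the morning dose on the Day 29 Visit", with the dosing row given as "Day 1 through Day 29 Visit".

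The notes to Table 11-4 apply the windows to scheduled and unscheduled visits alike. For efficacy, "if there are multiple measurements within a visit window, the measurement at the scheduled visit will be used". If there is no scheduled-visit value, the value closest to the target day is taken.

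Two other SAP passages bear on scope. Section 8.3.1.1.1 restricts the primary MMRM to data from visits in Period 1. Section 8.3 keeps values obtained after a subject discontinues treatment, up to the last scheduled Treatment Period visit, and refers to Appendix B for the windows.

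**The concern.** After the Day 29 Visit, a Part 2 subject is in Period 2, on TEZ/IVA alone. Protocol 9.3.1 says that this period exists to observe endpoints once VX-659 has washed out. A Part 3 subject is off all study drug. Under Table 11-4, an unscheduled measurement from those days can still become the Day 29 value of a subject who took VX-659 as planned but whose scheduled Day 29 value is missing or invalid. SAP 8.3.5 shows one way for this to happen: a sweat sample below 15 μL, or a result below 10 or above 160 mmol/L, is set to missing.

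The likely direction is toward no effect in the triple-combination arm. The controls lose no VX-659 effect after Day 29, because the Part 2 control stays on TEZ/IVA and the Part 3 control received placebo. The dilution therefore carries over to the between-group difference. Such a value would also appear as the subject's Day 29 response in the waterfall plots for ppFEV₁, CFQ-R and sweat chloride.

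**Working it through.** **1. Where the limits come from.** Each limit is the midpoint of adjacent target days.

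- Part 1, spirometry and sweat chloride: (29 + 33)/2 = 31
- Part 1, CFQ-R: (29 + 61)/2 = 45
- Part 2: (29 + 43)/2 = 36
- Part 3: (29 + 57)/2 = 43

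All four match Table 11-4. The limits are the result of a mechanical rule, not typing errors. Part 1 is tighter only because it has a Day 33 Visit.

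**2. Days off VX-659 at the upper limit**, for a subject who completes dosing: limit minus day of last dose, with the last dose on Day 27, 29 or 31.

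| Window | Limit | Last dose Day 27 | Day 29 | Day 31 |
|---|---|---|---|---|
| Part 1 spirometry, sweat chloride | 31 | 4 | 2 | 0 |
| Part 2 | 36 | 9 | 7 | 5 |
| Part 3 | 43 | 16 | 14 | 12 |
| Part 1 CFQ-R | 45 | 18 | 16 | 14 |

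**3. Who can be affected.**

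- A subject with a valid scheduled Day 29 value is not affected, because that value takes priority.
- A late scheduled Day 29 Visit is not off drug, because dosing runs to the actual visit.
- No scheduled visit for completers fills the gap. In Part 2 the next is Day 43 − 3 = Day 40, outside the Day 29 window. In Part 3, Safety Follow-up is at least 28 − 7 = 21 days after the last dose, so Day 27 + 21 = Day 48 at the earliest, and it is assigned by nominal visit.
- What remains is a completer with a missing or invalid Day 29 value, a later unscheduled value inside the window, and no other value closer to Day 29.

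**4. Size.** Planned triple-combination subjects: Part 2, 27 × 2/3 = 18; Part 3, 24 × 3/4 = 18. The 7-point change is from the sample-size statement (SAP 6.2.1.2). Three things are assumed, because the documents do not give them: a true change of 7 at both Day 15 and Day 29, the fraction f of subjects affected, and the share r of the effect retained. This is arithmetic on means, not a fitted MMRM.

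- Day 29 mean = 7 × [1 − f(1 − r)]
- Average of Days 15 and 29 = 7 × [1 − f(1 − r)/2]

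| f | r | Day 29 mean | Average |
|---|---|---|---|
| 1/18 | 0 | 6.61 | 6.81 |
| 1/18 | 0.5 | 6.81 | 6.90 |
| 2/18 | 0 | 6.22 | 6.61 |
| 2/18 | 0.5 | 6.61 | 6.81 |

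One fully washed-out value costs 7/18 = 0.39 at Day 29 and half of that, 0.19, in the average. For any endpoint that is 1/18 = 5.6% of the effect at Day 29 and 2.8% of the two-visit average. CFQ-R is reported at Day 29, so it gets no averaging.

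**5. Scale.** The plan states no SD. With an assumed SD of 6 to 8.6, the standard error of a mean of 18 is 6/√18 = 1.41 to 8.6/√18 = 2.03. A shift of 0.19 is then about 0.10 to 0.14 of a standard error.

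**The case against.** The strongest reply is that off-drug values are in the analysis by design. The endpoint is defined as change through the Day 29 Visit, with no on-treatment qualifier, and SAP 8.3 expressly keeps values obtained after treatment discontinuation. A reader might infer that the windows break an on-treatment definition of the endpoint. The documents contain no such definition, and that inference should not be drawn. For early stoppers the reply stands: their gap can be longer (a last dose on Day 22 gives 36 − 22 = 14 days in Part 2 and 43 − 22 = 21 in Part 3), and the plan accepts it. It does not cover a subject who finished Period 1 as planned, because that subject has not discontinued.

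It is also fair to say that the route is narrow. CFQ-R is not scheduled at the early-termination visit in any part, nor at Safety Follow-up in Parts 1 and 3, so a late CFQ-R in those parts would mostly come from a delayed Day 29 Visit. This limits the size of the problem but leaves the rule as written.

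A third argument is that the Period 1 scope in SAP 8.3.1.1.1 already excludes such values. Perhaps so, but Table 11-4 assigns them to the Day 29 visit, and a programmer following the table would include them. The two passages need reconciling.

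Different limits across parts might be read as a bias in themselves. They are not: each part is analysed separately.

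**Conclusion.** The point holds, and it is minor. For subjects who completed Period 1 dosing, Table 11-4 allows a value taken after VX-659 to be analysed as Day 29 in Parts 2 and 3, and for CFQ-R in Part 1. This is at odds with the stated scope of the primary MMRM and with the Day 31 limit that the SAP already uses for Part 1 spirometry and sweat chloride.

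The gaps of 7 and 14 days for Parts 2 and 3 assume a last dose on Day 29. They are not maxima: a Day 27 visit gives 9 and 16.

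A reader might infer that washout values enter the Day 29 results generally. They do not, because a valid scheduled value always takes priority. With one or two of 18 subjects affected and 0 to 50% of the effect retained, a 7-point mean becomes 6.2 to 6.8 at Day 29 and 6.6 to 6.9 on average, a small bias toward no effect. How often this would happen cannot be read from the documents, nor can the speed of washout.

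**What to change.** In SAP Appendix B, Table 11-4:

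- For subjects who completed Period 1 dosing, use the Part 1 spirometry rule (nominal Day 29 visit, otherwise (22, 31]) for spirometry, sweat chloride and CFQ-R in all parts.
- Keep early stoppers' post-discontinuation values under the current windows, as SAP 8.3 provides.
- Leave the Part 2 Day 43 window at (36, 50]. Starting it earlier would label early washout values as Day 43.
- List, but do not analyse, completers' unscheduled values that fall after the Day 29 limit and before the next window (in Part 2, Days 32 to 36).

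The rule still admits a value up to 4 days after a Day 27 last dose, as it already does in Part 1. A delayed Day 29 Visit is kept, because the nominal visit comes first.

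Cost: a table edit and a completer flag, which the disposition summary in SAP 8.2.1 needs anyway. An occasional late value becomes missing and is then handled under the MMRM's missing-at-random assumption.
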